If azacitidine or decitabine or INQOVI (oral decitabine) treatment is deemed by the investigator to possibly have contributed to an observed adverse event, the dose or schedule of hypomethylating agent treatment may be modified within a cycle and/or for subsequent cycles or temporary/permanent interruptions of HMA treatment may be decided by the investigator according to local practice and/or the US package insert guiding azacitidine or decitabine or INQOVI (oral decitabine) use.

- **Permanent discontinuation of MBG453 (sabatolimab) and HMA**

If the study treatment is interrupted for toxicities and the start of the subsequent study treatment cycle is delayed for more than 56 consecutive days (i.e. 2 planned consecutive cycles of study

treatment for both, HMA and MBG453 (sabatolimab) the participant should be discontinued from study treatment.

- **Permanent discontinuation of only one component MBG453 (sabatolimab) or HMA**

If **one component only** of the study treatment (HMA OR MBG453 (sabatolimab)) is discontinued for toxicities, then the treatment may continue with the other component of study treatment alone (MBG453 (sabatolimab) or HMA alone) as long as the participant benefits per investigator's judgement.

All dose changes must be recorded on the appropriate CRF.

Criteria for re-initiation of study drug MBG453 (sabatolimab) for adverse drug reactions

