## **12.3 Treatments (study treatment, concomitant therapies, compliance)**

The duration of exposure will be summarized for study treatment and for each study drug (MBG453 (sabatolimab) and HMA (azacitidine and decitabine and INQOVI (oral decitabine))). The dose intensity (computed as the ratio of actual cumulative dose received and actual duration of exposure) and the relative dose intensity (computed as the ratio of dose intensity and planned dose intensity) will be summarized for each study drug component by descriptive statistics.

The number of participants with dose adjustments (reductions for HMA only, interruption, or permanent discontinuation) and the reasons will be summarized by study treatment and by study drug.

Concomitant medications and significant non-drug therapies prior to and after the start of the study treatment will be summarized according to the Anatomical Therapeutic Chemical (ATC) classification system.

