2.4 Treatments (study treatment, rescue medication, concomitant therapies, compliance)

2.4.1 Study treatment / compliance

The duration of exposure will be summarized for study treatment and for each study drug (MBG453 (sabatolimab) and HMA (separately and combined together for all HMA)). The dose intensity (computed as the ratio of actual cumulative dose received and actual duration of exposure) and the relative dose intensity (computed as the ratio of dose intensity and planned dose intensity) will be summarized for each study drug MBG453 and for HMA individual component by descriptive statistics.

For MBG453, the actual cumulative dose in mg is the sum of “dose administered” from the eCRF of all cycles during the exposure of MBG453. For HMA (azacitidine, decitabine and INQOVI (oral decitabine), the actual dose in mg/m² in each cycle is the “dose administered” in mg during that cycle divided by the body surface area (BSA) at the beginning of the cycle using the weight measured before the infusion at that cycle. The actual cumulative dose in mg/m² is then the sum of all cycles. The following formula is used for BSA:

$$\text{BSA (m}^2\text{)} = \sqrt{\text{Weight (kg)} * \text{Height at screening (cm)} / 3600} \text{ (Mosteller formula)}$$

The duration considered for the derivation of the dose intensity and the relative dose intensity will be derived from the start date of study drug to the end of the last cycle initiated irrespective of date of death, last contact date for withdraw consent and cut-off date: the last exposure to study treatment (combination) will be the planned end date (Day 28) of the last cycle initiated with MBG453 and/or HMA, whichever is the latest. Details are provided in section [5. Appendix](#).

The relative dose intensity is then comparing the actual dose intensity during subject's exposure with the protocol planned dose of 800 mg Q4W for MBG453 and 20 mg/m² for decitabine, 75 mg/m² for azacitidine and Decitabine Oral (INQOVI) (100mg cedazuridine / 35mg decitabine), e.g. if a subjects received 300 mg Q2W on average throughout the study, the relative dose intensity for this subject is 0.75.

Dose reductions, interruptions or permanent discontinuations

The number and percentage of subjects with any dose changes of MBG453 (incl. interruptions, or permanent discontinuations) and the reasons will be presented.

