5.4 Date of last administration of study treatment (combination)

The date of last administration of study treatment (or end date of study treatment) is defined as the last date when the last non-zero dose of any last component of the study treatment (MBG453 (sabatolimab) in combination with HMAs (IV/SC/Oral)) is administered.

5.5 Date of last exposure to HMA and investigational drug and date of last exposure to study treatment (combination)

One planned cycle length is 28 days. HMA drugs are planned to be administered every cycle between Day 1 and Day 9 with different schedules. MGB453 is administered every 4 weeks, on Day 8 out of a 28 days cycle, unless there was a toxicity leading to a dosing interval increase.

As treatment is given in cycles, the date of last administration of study treatment is not considered the date of last exposure but instead the planned end date of the last cycle in which the last non-zero dose was given.

The **date of last exposure to MBG453** is therefore calculated as:

- Minimum (last date of administration of investigational drug + 27 days, date of death, last contact date in case subject is lost to follow-up), as MBG453 injections is given Q4W (in case of change to Q8W, the cycle would end after 55 days)

The **date of last exposure to HMA** drugs is calculated as:

The date of last exposure to azacitidine

- Minimum (last date of administration of azacitidine + 20 days, date of death, last contact date in case subject is lost to follow-up) as azacitidine is given daily every cycle during

7 days at the beginning of each cycle (between Day 1 to Day 9) (total cycle length 28 days).

The date of last exposure to decitabine

- Minimum (last date of administration of decitabine + 22 days, date of death, last contact date in case subject is lost to follow-up) as decitabine is given daily every cycle during 5 days at the beginning of each cycle (between Day 1 to Day 5) (total cycle length 28 days).

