The **date of last exposure to study treatment (combination)** is calculated as the minimum date between the end date of the last cycle initiated with any component of the study treatment, the date of death and the last contact date in case subject is lost to follow-up. The end date of the last cycle initiated is the planned end date (Day 28) of the last cycle initiated where MBG453 and/or HMA were last administered or the date of the last administration of a non-zero dose of any last component of the study treatment (MBG453, HMA), whichever is the latest. The duration of exposure to study treatment (combination) will be calculated as follow: date of last exposure to study treatment (combination) - date of first administration of study treatment (combination) + 1.

The planned end date of a cycle (Day 28) will be applicable even if this date goes beyond the data cutoff date (it should not be truncated to the date of data cutoff).

5.6 Duration of study treatment (combination) used to calculate the dose intensity and the relative dose intensity

For the calculation of the dose intensity and relative dose intensity, the cycle-based exposure to study treatment (combination) will be derived from the date of first administration of study treatment (combination) to the actual or planned end date of the last cycle initiated (whichever is the latest) irrespective of date of death, last contact date for withdraw consent and cut-off date.

The start date of the first cycle initiated is the first date when a non-zero dose of HMA.

The end date of the last cycle initiated is the planned end date (Day 28) of the last cycle initiated where MBG453 and/or HMA were last administered or the date of the last administration of a non-zero dose of any component of the combination, whichever is the latest.

The duration of study treatment in days used to derive the dose intensity and the relative dose intensity will be calculated as follow: end date of the last cycle initiated – date of first administration of study treatment (combination) + 1.

The planned end date of a cycle (Day 28) will be applicable even if this date goes beyond the data cutoff date, the date of death or the date of last contact date for withdraw consent (it should not be truncated to the date of data cutoff, the date of death or the date of last contact date).

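### Each drug's dose intensity is divided by the combination period, so when one drug is continued alone the other's relative dose intensity mixes early stopping with dosing while on drug

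*SAP*

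**What the plan says.** Protocol 12.3 gives the definition: "The dose intensity (computed as the ratio of actual cumulative dose received and actual duration of exposure". It adds that DI and RDI "will be summarized for each study drug component by descriptive statistics". SAP 2.4.1 repeats the definition and takes the sabatolimab numerator from the doses "of all cycles during the exposure of MBG453".

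The denominator is set in two places.

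- SAP 2.4.1 says that it is "derived from the start date of study drug to the end of the last cycle initiated", and that "the last exposure to study treatment (combination) will be the planned end date (Day 28) of the last cycle initiated with MBG453 and/or HMA", taking the later of the two.
- SAP 5.6 says that "the cycle-based exposure to study treatment (combination) will be derived from the date of first administration of study treatment (combination". It uses the same end date and rules out truncation at death, at last contact after withdrawal of consent, or at data cut-off.

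SAP 5.5 separately derives a last-exposure date for each drug. For sabatolimab it is "Minimum (last date of administration of investigational drug + 27 days, date of death, last contact date in case subject is lost to follow-up". SAP 5.6 does not use these dates for DI or RDI.

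On stopping one drug for toxicity, protocol 6.5 says "then the treatment may continue with the other component of study treatment alone". Protocol 6.1.4 allows either component alone more generally, and protocol section 3 and SAP 1.1 allow it in the extension phase.

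**The concern.** A numerator that belongs to one drug is divided by a duration that belongs to two. While both drugs are given to the end, the two durations agree and nothing is lost. Once a participant stops sabatolimab and stays on the HMA, every further HMA cycle lengthens the sabatolimab denominator and adds nothing to the numerator. The same happens to the HMA figure when sabatolimab is continued alone.

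The resulting RDI cannot separate two different histories: full dosing followed by an early stop, and reduced delivery while on drug. The primary objective is the safety of sabatolimab 800 mg every 4 weeks with an HMA. A reader of the adverse event tables will look to the RDI to see how fully that dose was delivered.

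**Working it through.** **Inputs**

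- Planned sabatolimab intensity: 800 mg per 28 days (SAP 2.4.1).
- Cycle length: 28 days (SAP 5.5).
- Core phase: 13 cycles, 13 × 28 = 364 days (protocol Table 8-1). A further 13 extension cycles make 26.
- RDI = (cumulative dose / duration) / (800 / 28).

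**The SAP's own example.** 300 mg every 2 weeks: (300/14) / (800/28) = 0.75. This reproduces the figure in SAP 2.4.1.

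**General form.** Take k full doses in cycles 1 to k, with HMA given through cycle m.

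- As written: (800k / 28m) / (800/28) = k/m.
- Over sabatolimab's own cycles: (800k / 28k) / (800/28) = 1.00.

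| Sabatolimab doses | Last HMA cycle | RDI as written | RDI over own cycles |
|---|---|---|---|
| 13 | 13 | 1.00 | 1.00 |
| 9 | 13 | 0.69 | 1.00 |
| 6 | 13 | 0.46 | 1.00 |
| 3 | 13 | 0.23 | 1.00 |
| 13 | 26 | 0.50 | 1.00 |
| 6 | 26 | 0.23 | 1.00 |

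For 6 of 13, written out: 4800 mg / 364 days × 28 = 369 mg per 28 days, and 369/800 = 0.46. Over 6 × 28 = 168 days the figure is 800 mg per 28 days.

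**Comparison with a stretched interval.** Seven doses every 8 weeks across 13 cycles, with both drugs continued, score 7/13 = 0.54 as written. A participant who missed no dose while on sabatolimab (0.46) therefore ranks below one who was dosed every 8 weeks throughout.

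**Which end of the period matters.** Starting at the first sabatolimab dose (Day 8) and keeping the combination end date gives 364 − 7 = 357 days and (4800/357) / (800/28) = 0.47. The end date drives the result. The start-date difference between 2.4.1 and 5.6 is worth about 7 days.

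**The HMA.** HMA given in 3 cycles, with sabatolimab alone to cycle 13, gives an HMA RDI of 3/13 = 0.23.

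**Effect on a summary mean.** The documents give no share of participants continuing one drug alone, so the shares here are assumed. If a share f stops after 6 doses and takes HMA to cycle 13, and all others have RDI 1.00, the mean is (1 − f) + f × 6/13. For f = 10%, 20%, 30% and 50% this is 0.95, 0.89, 0.84 and 0.73.

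**Whether the SAP 5.5 dates would serve as a replacement.** They would not.

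- Truncation at death: with six doses on Day 8 of cycles 1 to 6, the last falls on study day 5 × 28 + 8 = 148. Death 10 days later gives 158 − 8 + 1 = 151 days and (4800/151) / (800/28) = 1.11.
- Cycle end: azacitidine on Days 1–7 ends on Day 7 + 20 = 27, and decitabine on Days 1–5 ends on Day 5 + 22 = 27, one day short of the cycle. Azacitidine finishing on Day 9 ends on Day 29.
- Partial cycle: azacitidine stopped after Day 3 of a single cycle ends on Day 23, giving (3/23) / (7/28) = 0.52, against 3/7 = 0.43 over 28 days.

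**The case against.** The strongest reply is that the combination period is deliberate. SAP 5.6 is a separate section written for this purpose, it follows the drug-specific dates of 5.5, and it has its own truncation rules. The worked example in 2.4.1 is framed as an average over the whole study. An RDI over the whole course answers a fair question: how much of the planned regimen was delivered. That stands, and it is why the figure should be kept under its own label.

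Three stronger readings are tempting, and the documents do not support them.

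- A reader might infer that 5.6 overrides a drug-specific denominator set in 2.4.1. But 2.4.1 itself sets the combination end date. The tension lies within 2.4.1, and 5.6 carries it out.
- A reader might infer an undeclared departure from the protocol. SAP section 4 has two redacted entries, so nothing can be said about what it omits. Protocol 12.3 mentions duration both for study treatment and for each drug without saying which one is the denominator. The per-drug reading is the natural one, but it is not spelled out.
- A reader might infer that early stopping is hidden. It is not: duration of exposure is summarised for each drug, and permanent discontinuations are tabulated with reasons. What those tables cannot do is recover RDI while on drug from an RDI summary that has already been diluted.

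The other side is also right that the output is descriptive, in 39 participants, with no hypothesis test.

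**Conclusion.** The point holds as a minor one. As specified, the per-drug RDI combines time off that drug with delivery while on it, for any participant who continues the other drug alone. For an individual the distortion is k/m against 1.00: 0.46 for 6 of 13 cycles and 0.23 for 3 of 13. These figures assume that every planned 800 mg dose was given until sabatolimab stopped and that the HMA then continued without a break. The effect on the reported summary depends on the number who continued one drug alone, which the documents do not give.

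Participants who receive both drugs to the end are unaffected. So are the exposure-duration summaries, the safety endpoint itself and all efficacy analyses.

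**What to change.** In SAP 2.4.1 and 5.6:

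1. Report DI and RDI for each drug over that drug's own cycle-based exposure: from Day 1 of the first cycle in which it was given to planned Day 28 of the last cycle in which it was given, extended by 28 days if sabatolimab was then on the 8-week interval. Do not truncate at death, loss to follow-up or cut-off, and do not reuse the SAP 5.5 last-exposure dates.
2. Keep the combination-period RDI as a second measure, labelled as covering the whole treatment course.
3. Reconcile the start date, which 2.4.1 takes from the study drug and 5.6 from the combination.

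The cost is one derived variable per drug, an extra row in a descriptive table and the SAP wording. The current addendum is dated after database lock, so the addition should be recorded as made after lock. With no hypothesis test it raises no error-rate question. The downside is that a drug-specific RDI no longer reflects early stopping, or doses withheld just before discontinuation, and so leans upwards. The labelled combination figure and the discontinuation and exposure-duration tables still show those.

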5.7 Windows for multiple assessments

Note: As per CTT discussion, It was suggested to use CRF visits for ECOG and ePROs and remove the visit window from the SAP. It is acknowledged that CRF visits might be delayed,

which is not unusual from a medical perspective. Additionally, the "End of Treatment" visits are subject-specific based on the study design. These point should be mentioned in the footnotes of the respective tables.

5.8 Last contact date

The last contact date will be used for censoring of subjects in the analysis of overall survival.

The last contact date is defined as the latest complete date from the below list on or before the data cut-off date ([Table 5-1](#)). The cut-off date will not be used for last contact date, unless the subject was seen or contacted on that date. No date post cut-off date will be used.

Completely imputed dates (e.g. the analysis cut-off date programmatically imputed to replace the missing end date of a dose record) will not be used to derive the last contact date. Partial date imputation is allowed for event (death)/censoring only if coming from the 'Survival' eCRF.

The last contact date will be derived for subjects not known to have died at the analysis cut-off using the last complete date among the following:

Table 5-1 Last contact date data sources

| Source data | Conditions |
|--|---|
| Date of enrollment | No condition |
| Last date subject was known to be alive from Survival Follow-up page | Subject status is reported to be alive or unknown |
| Start/End dates from further antineoplastic therapy | Non-missing medication/procedure term |
| Start/End dates from drug administration record | Non-missing dose |
| Response assessment date | Response marked as 'done' |
| Laboratory █ collection dates | Sample collection marked as 'done' |
| Vital signs date | At least one non-missing parameter value |
| ECOG performance status date | Non-missing performance status |
| Start/End dates of AE | Non-missing verbatim term |

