### **9.1.5 Extension phase**

Patients completing core phase of 12 months and requiring continuation of study treatment (by investigator decision) beyond 1 year will enter the extension phase. For patients that will receive treatment in the extension phase, they are allowed to continue treatment with MBG453 and

azacitidine/decitibine/INQOVI (oral decitibine), azacitidine/decitibine/INQOVI (oral decitibine) alone, or MBG453 alone.

Additionally, for participants who discontinue any study treatment for reasons other than documented disease progression, death, lost to follow-up, or withdrawal of consent, will enter the extension phase.

Efficacy assessments (hematology and bone marrow aspirate/biopsy) should follow [Table 8-1](#). Response assessments must continue to be performed every 3 cycles as per hematology assessment and at least every 6 cycles as per bone marrow assessment or as clinically indicated until documented disease progression/relapse (per IWG criteria [Table 8-2](#)), death, lost to follow-up, or withdrawal of consent.

Drug will be supplied as per [section 6.1.4](#) Also patients who will receive HSCT will be included in the extension phase. Patients will be followed up for efficacy and safety as per [Table 8-1](#) up to 24 months post last patient first treatment. Once they complete the extension phase or end treatment due to progression or any reason excluding HSCT, death, lost to follow up, or withdrawal of consent, patients will enter the post-treatment safety follow up. Participants on the extension period can be contacted by telephone every 6 cycles (24 weeks) to follow-up on their survival status.

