#### **9.1.6 Post treatment safety follow up period**

Post treatment safety follow up period is for 150 days for safety and until end of study for survival follow up.

All patients on the study should enter the post treatment safety follow up period. Patients can enter the post treatment safety follow up period any time during the study based on discontinuation or completion of prior core phase or extension phase. Reasons for entering the post treatment safety follow up period can be completing the extension phase or ending treatment due to progression. Any new antineoplastic therapies and transfusions that have been started since the previous contact will be collected. HSCT information will also be collected during these phone calls and [REDACTED] will be collected as part of the safety follow up. Participants on the post treatment safety follow up period can be contacted by telephone every 6 cycles (24 weeks) to follow-up on their survival status.

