A total of 39 subjects were enrolled in this study. Subjects were recruited from sites within the United States. No pre-treatment stratification is planned. The investigator or designee must ensure that only subjects who meet all the inclusion and none of the exclusion criteria are enrolled in the study.

There are 4 types of periods/phases: Screening phase, core phase, extension phase and post treatment safety follow-up

Screening phase: A signing of written informed consent obtained through day 1 of enrollment (from up to 28 days of period prior to core phase start date).

[figure not shown]
Core phase: A 12 months of treatment period is a **core phase**

Extension phase: Extension phase for efficacy and/or survival status (up to 24 months of last subject enrolling) or in addition to core phase (12 months), an additional 12 months of treatment period is **extension phase**.

Post treatment safety follow up: Post treatment safety follow-up monitoring for adverse events (AEs) for 30 days following the last dose of azacitidine or decitabine or INQOVI (oral decitabine), or 150 days following the last dose of MBG453 (sabatolimab), whichever is later.

Figure 1-1 Study design

Study design

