1.2 Study objectives and endpoints

Main objective of this proposed study is to describe and evaluate safety and efficacy of MBG453 (sabatolimab) in combination with FDA approved HMA of investigator's choice in a single-arm, non randomized, open label, phase II multi-center US study.

[figure not shown]
Objectives and related endpoints are described in [Table 1-1](#) below.

Table 1-1 Objectives and related endpoints

Cut-off date: For analysis of the primary and secondary objectives and endpoints, 12 months post LPFT will be considered as cut-off date. Additionally, for OS of 24 months, the cut-off date will be considered as 24 months post LPFT.

| Objective(s) | Endpoint(s) |
|--|---|
| Primary Objective 
 To assess the safety profile of MBG453 (sabatolimab) 800 mg (every 4 weeks) given in combination with HMA (IV/SC/Oral) by 12 months | Endpoint for primary objective Incidence and severity of AEs and SAEs, changes in laboratory values and vital signs |

| Secondary Objectives | Endpoints for other secondary objectives |
|--|--|

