2.7.1.3 Overall Survival

Overall Survival (OS) rate is defined as the proportion of subjects alive time from the date of enrollment (cycle 1 day 1) to date of death due to any cause.

If a subject is not known to have died, then OS will be censored at the latest date the subject was known to be alive (on or before the cut-off date). All deaths will be taken into account whenever the death occurred, i.e. even after new anti-neoplastic therapy, HSCT, interruptions, or discontinuation of study treatment due to any reason.

The OS censoring reason will be summarized as 'Alive' or 'Lost to follow-up'. Subjects not known to have died will have the censoring reason 'Lost to follow-up' if the reason for discontinuation from study is 'Lost to follow-up' or 'Withdrawal of consent'.

Otherwise, subjects will have the censoring reason 'Alive'.

OS will be analyzed using the Kaplan-Meier Product-Limit method. Estimates of the 25th, median and 75th percentile of the OS and their 95% confidence intervals will be provided, Kaplan-Meier curves will be produced, if applicable.

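### SAP 5.8 discards proof of life after the overall survival cut-off while deaths dated before it still count, which biases the late part of the LPFT+12 curve modestly downward

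*SAP*

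**What the plan says.** - **Cut-offs.** SAP 1.2 fixes calendar cut-offs: "12 months post LPFT will be considered as cut-off date", and 24 months post LPFT for the additional OS analysis. SAP 2.7.1 also plans the secondary endpoints on the complete available data.
- **Living subjects.** SAP 5.8 takes the latest complete date among the sources in its Table 5-1. It adds "The cut-off date will not be used for last contact date, unless the subject was seen or contacted on that date" and "No date post cut-off date will be used".
- **Deaths.** SAP 2.7.1.3 says "All deaths will be taken into account whenever the death occurred". It sets no condition on when the death became known.
- **Survival contacts.** Protocol 9.1.6 says participants "can be contacted by telephone every 6 cycles (24 weeks) to follow-up on their survival status". Protocol 9.1.5 has the same interval for the extension. Neither document describes a survival sweep at a cut-off.
- **Timing.** SAP 2.1 replaces separate reports by one final report. Protocol 3.1 lets the study run to 29 months after the last enrolment. The SAP's document history dates the current text 07-Feb-2025, after database lock.

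**The concern.** Take two subjects last contacted 150 days before a cut-off. One dies in the gap. The next call brings a death date before the cut-off, and the subject is an event. The other answers that same call alive. The call falls after the cut-off, so the subject is censored 150 days early and leaves the risk set. A subject who dies after the cut-off is treated the same way, although that death proves survival to the cut-off.

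Within the last contact gap, survivors are removed and deaths are kept. Kaplan-Meier needs censoring that is unrelated to outcome, and here it is not. The risk set is too small when those deaths occur, so the curve falls too fast. SAP 2.7.1.3 reports the OS quartiles, the median and the curve, and these are the outputs at stake. Had the report been written at LPFT+12, the later calls would not have existed. They are in the database now because the cut-offs are applied retrospectively.

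**Working it through.** **The plan's own figure.** The documents give no OS rate, event count or precision, so there is no OS figure to reproduce. The only design calculation is for an adverse event rate: 1.96² × 0.30 × 0.70 / 0.10² = 80.67, rounded up to 81. It reproduces, and has no bearing here.

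**The two rules.** Let E be enrolment, C the cut-off, L the last contact on or before C, and D the death date. If D ≤ C, both rules give an event at D − E. A subject alive at C with later proof of life is censored at L − E under SAP 5.8 and at C − E under the alternative. The curve is S(t) = ∏(1 − d/n). Moving survivors from C back to L lowers n and leaves d unchanged, so each affected factor falls.

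**Where on the curve this acts.** The longest scheduled gap between survival calls is 6 × 28 = 168 days, or 168 / 30.4375 = 5.5 months. At LPFT+12 the last subject enrolled can lose time only after month 12 − 5.5 = 6.5. Subjects enrolled earlier lose time later, up to month 12 + 17 = 29 if accrual took 17 months. Month 12 is therefore touched only through the last subjects enrolled, while months 12 to 24, where the median may fall, are touched by most. At LPFT+24 the affected zone starts at 24 − 5.5 = 18.5 months, so month 24 is likewise near its beginning.

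**Inputs to the simulation.**
- 39 subjects (SAP 1.1).
- Median OS 12 to 24.5 months. This is an assumption; the protocol cites a median under 1 year from HMA initiation (1.1) and 24.5 months with azacitidine (4.3.1).
- Accrual 12 to 17 months. This is an assumption; no one was enrolled on 01-Apr-2021 and recruitment stopped on 30-Sep-2022, so the maximum is about 18 months.
- Median time on treatment 8 months. This is an assumption, taken from the exposure quoted in Protocol 4.3.2.
- Off-treatment contacts either at Days 30, 90 and 150 and then every 168 days, or every 60 days.

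**Results, SAP rule minus alternative rule.**

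| Output | Days 30/90/150, then 24-weekly | Every 60 days |
|---|---|---|
| Median OS, LPFT+12 | −0.1 to −1.1 months | −0.05 to −0.4 months |
| Month-18 OS, LPFT+12 | −2 to −3.5 points | about −1 point |
| Month-12 OS, LPFT+12 | about −0.5 points or less | about −0.1 point |
| Month-24 OS, LPFT+24 | about −0.5 points or less | about −0.1 point |

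The median shift applies where the curve reaches 50%.

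Runs with 16-month accrual and a death hazard assumed three times higher off treatment show how far back survivors are censored. With 8 months on treatment, the mean distance from the LPFT+12 cut-off is 47 to 58 days under the first pattern and 25 to 27 days under the second. In those runs the alternative rule gave an estimate within about 1 point of the true value, which is simulation noise.

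**The case against.** **Contacts are more frequent than the survival calls.** A reader might infer that survival is learned only every 24 weeks off treatment. The documents do not support that. There is a Day 30 visit and there are Day 90 and Day 150 calls (Protocol 10.1.1). Hematology continues every 2 months after discontinuation (9.1.1) or every 3 cycles in the extension (9.1.5). Table 5-1 accepts laboratory, response, adverse event, vital sign, ECOG and further-therapy dates. This stands, and it shortens the gap for some subjects. It does not close it. Transfusion dates are not a Table 5-1 source. The follow-up page of Protocol Table 8-1 lists no hematology or response visits. Protocol 9.1.5 stops response assessment at progression, whereas 9.1.1 continues hematology to the end of the study.

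**The asymmetry is partly inferred.** The sentence on deaths in SAP 2.7.1.3 goes on to speak of new therapy, transplant and treatment discontinuation, not of late reporting. SAP 5.8 speaks of subjects not known to have died at the cut-off, which could mean known at that time. On that reading late-reported deaths would drop out too. The text does not settle it. However, nothing in the SAP tests when a death became known, and with a locked database a death date before the cut-off is on the ordinary reading an event.

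**Other analyses limit the damage.** OS on complete data is also planned, and no hypothesis is tested. Both are true. The LPFT+12 median, quartiles and curve remain planned outputs.

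**The shift is small against sampling error.** The sampling standard deviation of the LPFT+12 median is about 2.4 to 3.8 months, and that of the landmark rates about 6 to 8 points. This stands for size. The error nevertheless always goes in one direction and can be removed.

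**Conclusion.** The point holds as a modest, one-directional error in the late part of the LPFT+12 OS curve, of the size tabulated above. It depends on the assumed survival, accrual, treatment time and contact pattern, and on late-reported deaths being counted.

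Two stronger readings should be avoided. First, the 24-month OS objective is not compromised. It has its own LPFT+24 cut, where the month-24 rate moves by about half a point or less; one subject in 39 is 1/39 = 2.6 points. Even if the 24-weekly call were the only off-treatment contact, the landmark shifts would be 0.3 to 0.7 points. Second, reading month 24 off the LPFT+12 curve can give differences of 5 to 11 points, but that is not a fair measure. With 12-month accrual essentially no one is at risk at that point, and the larger differences come from carrying the curve past its data.

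**What to change.** In SAP 5.8, replace the sentence barring dates after the cut-off with:

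*A subject with any documented evidence of being alive after the cut-off, including a death dated after the cut-off, is censored at the cut-off date; all other subjects not known to have died are censored at their last contact date on or before the cut-off.*

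The preceding sentence, which allows the cut-off date only if the subject was seen or contacted that day, needs the same exception or the two will conflict. SAP 2.7.1.3 can stay, because a subject known to be alive later was alive on the cut-off date. Report the present rule as a sensitivity analysis.

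The cost is one programming line and one extra table, from data already held. Moving survival calls to the cut-offs is not an option: recruitment stopped on 30-Sep-2022, both cut-offs have passed, and the database is locked.
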